The study spanned three months, with pre-tests conducted within the first two weeks befor the first session and post-tests within two weeks after the 36th session. Functional physical fitness and quality of life assessments were conducted for both groups befor and after each session. Upon completion of the overall program, the researchers provided comprehensive feedback on the study's results.

Exercise Protocol:

Both groups initially engaged in modal rate-intensity exercise. The experimental group underwent a 12-week intervention program, consisting of 3 sessions per week, totaling 36 sessions. Each session lasted 60 minutes and included the following components:

Warm-up exercises (10-15 minutes)

Main exercise activity (30 minutes)

Cool-down exercises (5-10 minutes), with a 10-minute break in between To mitigate potential risks associated with exercise training, blood pressure measurements were taken befor each session. Participants engaged in exercises under the guidance of research personnel. If participants felt unwell on a given day, they were allowed to skip the session. In case of any discomfort during the activity, the training was immediately halted.

Hardware and Software Setup:

The intervention utilized a touch-enabled 11-inch tablet computer loaded with the research game system, serving as the interface for participants to interact with the VR interactive game. A laptop computer facilitated the connection between the tablet and projector. The game content could only be downloaded and used on the tablet or Android smartphones. To allow elderly participants to see the game's effectiveness during the activity, the tablet was wirelessly connected to the laptop and projected onto a white wall in the same Wi-Fi environment.

Game Implementation:

The game design included four aircraft, each representing a participant in the group. Before starting the game, the game and sensors were paired via Bluetooth. The sensors were securely placed on the waist belt at the lumbar spine level. Participants underwent posture corrections, including left-right bending, forward bending, and backward leaning, to ensure accurate sensor data capture. Once all participants completed the calibration, the game training for that session began, with three game records per activity.

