This study aims to understand the impact of intervention on the functional fitness and quality of life of elderly participants befor and after the intervention. The assessment tools used include functional fitness tests and a quality of life questionnaire, along with the collection of basic participant information. Both groups underwent pre-tests befor the intervention, which included a fall risk assessment, functional fitness assessment, and quality of life satisfaction survey. After completing the 12-week, 36-session intervention, post-tests were conducted to measure the effectiveness of the intervention.

1. Basic Participant Information:

Includes gender, age, exercise habits, self-perceived health status questionnaire, and Body Mass Index (BMI).

2. Functional Fitness Tests:

(a) Chair Stand Test:

Measures lower body strength/endurance.

Participants sit in a chair without armrests and stand up as many times as possible within 30 seconds.

(b) Chair Sit and Reach Test:

Assesses lower body flexibility.

Participants sit on the edge of a chair with one knee bent at 90 degrees and try to reach their toes with their hands. The distance between the fingertips and toes is measured.

(c) 8-Foot Up-and-Go Test:

Evaluates agility and dynamic balance.

Participants sit in a chair, stand up upon hearing a signal, walk around a designated point 8 feet away, and return to the chair. The time taken to complete the task is recorded.

(d) 2-Minute Walk Test:

Measures aerobic endurance.

Participants walk in place for 2 minutes, and the number of times the knees are lifted to a specific height is counted.

3. Quality of Life Questionnaire:

Administered using the "Taiwanese version of the World Health

Organization Quality of Life Questionnaire-Brief Form

(WHOQOL-BREF Taiwanese version)."

Consists of 28 questions divided into four domains: physical health, psychological health, social relationships, and environment.

Each question is scored on a Likert scale ranging from 1 (very poor) to 5 (very good), with higher scores indicating better quality of life. Demonstrates good reliability with Cronbach's α and split-half reliability of 0.92 and 0.93, respectively. Section 6 Data Processing and Statistical Analysis

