After data collection, the collected data will be coded, documented, and analyzed using the Statistical Package for the Social Sciences (SPSS) 19.0 Chinese version software. Both descriptive and inferential statistics will be employed. A significance level of p < .05 will be used to determine statistical significance.

1. Descriptive Statistics:

Categorical variables of demographic data for both experimental and control groups will be presented as percentages, while continuous variables will be described using means and standard deviations.

2. Inferential Statistics:

(a) Independent t-test or Mann-Whitney U test:

Analyze the differences between the experimental and control groups in variables such as balance function, muscle strength, flexibility, cardiovascular capacity, and quality of life befor intervention. A Shapiro-Wilk test will be conducted to check for normal distribution. If the data is normally distributed, an independent t-test will be used; otherwise, the Mann-Whitney U test will be employed.

(b) Chi-Squared Test:

Analyze the homogeneity of basic demographic characteristics (age, gender, education level, marital status), exercise habits, duration of each exercise session, and experience of falling in the past year between the two groups.

(c) Dependent Samples t-test or Wilcoxon Signed Rank Test: Analyze the differences in variables such as balance function, muscle strength, flexibility, cardiovascular capacity, and quality of life within each group 之前 and after the intervention. A Shapiro-Wilk test will be conducted to check for normal distribution. If the data is normally distributed, a dependent samples t-test will be used; otherwise, the Wilcoxon signed rank test will be employed.

(d) ANCOVA Analysis using Intention-to-Treat Analysis:

ANCOVA will be employed to compare the post-test scores between the experimental and control groups while controlling for pre-test scores. This analysis will utilize intention-to-treat principles.

[figure not shown]

Figure 8. Flowchart of the application of virtual reality interactive games

to the lower limb balance of community elders

Research Results

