This study involved the intervention of the experimental group using virtual reality interactive games, while the control group underwent exercise interventions led by original instructors. Both groups participated in modal rate-intensity sessions three times a week for 12 weeks, totaling 36 sessions. Testing was conducted befor and three months after the completion of the program. A total of 84 participants were recruited from two community care activity centers in Taipei City, but 14 participants were excluded due to personal reasons or inability to consistently monitor data due to illness. Ultimately, data from 70 participants who completed at least 30 sessions were analyzed.

Regarding participant attrition, the experimental group initially recruited 35 participants. However, during the 12-week, 36-session program, five participants were absent for over one-third of the sessions (12 sessions) due to health issues or personal preferences, rendering their data unusable. The experimental group experienced a dropout rate of 14.28%. The control group initially recruited 35 participants, but only 33 completed the post-intervention assessment. Two participants were excluded from the analysis due to absence for over one-third of the sessions. The dropout rate for the control group was 8.57%. Both groups had dropout rates within the predetermined range of 15% set befor the study.

The study spanned 36 sessions from February 13th to May 31st, [insert year]. Data from participants who attended less than 12 sessions were

excluded from statistical analysis. Thus, statistical analysis was conducted on data from 30 participants in the experimental group and 33 participants in the control group.

Section 1: Participant Demographics

This study recruited a total of 70 participants, with 35 participants in both the experimental and control groups. Among them, 63 participants completed the entire study, with 30 participants in the experimental group and 33 participants in the control group. The average age of the experimental group (30 participants) was 77.7 years, with the majority being female (96.7%) and married (90.0%). See Table 4-1 for details. Assessment of demographic data in both groups showed no significant differences. Independent samples t-tests or Mann-Whitney U tests and chi-squared tests were used to analyze demographic data, revealing no significant differences between the two groups' demographic characteristics, as shown in Table 2.

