		Control group	t value (p) or Z value (p) or		
	Test group (N=30)	(N=33)	Chi-square value $(p)^*$		
Demographic					
variables					
age	77.7 ± 5.8	74.4 ± 8.3	1.78 (0.080)‡		
Gender: emale)	29 (96.7%)	30 (90.9%)	0.88 (0.614)		
marriage			2.00 (0.615)		
unmarried	0 (0%)	2 (6.1%)			
Married	27 (90.0%)	27 (81.8%)			
Widowed	3 (10.0%)	4 (12.1%)			
BMI	27.0 ± 3.5	25.4 ± 3.8	1.77 (0.077)§		
height	150.5 ± 5.2	152.5 ± 7.0	-1.29 (0.201)†		
weight	61.0 ± 6.5	59.2 ± 9.8	0.86 (0.393)∫		

Table 2 Basic information table of elderly subjects of virtual reality

interactive games

‡Shapiro-Wilk test: *P*=0.055 , Using independent sample t test

Based on descriptive statistics, it was confirmed that in the control group, the highest education level was junior high school graduation, with 13 individuals (43.3%), followed by 11 individuals (36.7%) who graduated from elementary school. All elderly participants had a habit of exercising, with 30 individuals (100%) regularly attending exercise classes at the activity centers. Seven individuals (23.3%) reported experiencing falls in the past year. Regarding exercise frequency, 6 individuals (20.0%) exercised fewer than three days per week, while 24 individuals (80.0%) exercised at least three days per week. Moreover, all participants exercised for at least 30 minutes each time. In the control group, the highest education level was high school or vocational school graduation, with 14 individuals (42.4%), followed by 10 individuals (30.3%) who graduated from junior high school. Thirty-two individuals (97.0%) had a habit of exercising, primarily by attending exercise classes at the activity centers. Eight individuals (24.2%) reported experiencing falls in the past year. Regarding exercise frequency, 11 individuals (33.3%) exercised fewer than three days per week, while 22 individuals (66.7%) exercised at least three days per week. The majority, 30 individuals (90.9%), exercised for at least 30 minutes each time. See Table 3 for details.

	Test group (N=30)	Control group	Chi-square value (p)
		(N=33)	
Education level			11.742 (0.014)
Not reading	0 (0%)	2 (6.1%)	
Elementary school	11 (36.7%)	4 (12.1%)	
Junior high school	13 (43.3%)	10 (30.3%)	
High school	6 (20.0%)	14 (42.4%)	
University	0 (0%)	3 (9.1%)	
Exercise habits			1.949 (0.321)
No habit	0 (0%)	1 (3.0%)	
Less than 3 times a week	6 (20.0%)	10 (30.3%)	
More than 3 times a week	24 (80.0%)	22 (66.7%)	
Each exercise time			6.326 (0.039)

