This study primarily utilized virtual reality interactive games for training. It employed a three-axis inertial sensor to monitor body angle changes during exercise. Older adults wore a waist protector embedded with sensors, which connected via Bluetooth to control a virtual aircraft in the game. Participants moved their bodies forward, backward, left, and right to collide with asteroids and coins in different directions, challenging their balance with varying levels of difficulty such as standing with feet parallel, slightly squatting with feet parallel, and standing with feet apart. implie m itionally, participants were required to raise their hands and perform stretching and bending movements in sync with body movements in the game. This not only increased upper body movement opportunities but also effectively maintained body balance, reducing the risk of falls during

the game. Researchers like Fang et al. (2016) found that using virtual reality Wii Fit games for training for more than 6 weeks can improve dynamic balance ability in older adults.

In this study, a custom-designed virtual airplane game allowed elderly participants in community center activities to effectively train balance and improve flexibility during exercise. By following game instructions for forward and backward movements, participants could earn scores and complete tasks successfully. After 36 sessions, significant improvements were observed in elderly participants who engaged in virtual reality interactive games, particularly in the 2-minute step test (p<0.001) and left and right chair stands (p<0.001, p=0.003). ANCOVA analysis revealed differences in physical fitness (except for the 30-second chair stand) and quality of life, with effect sizes (partial eta squared) ranging from 0.011 to 0.267, indicating moderate to substantial intervention effects. These findings demonstrate that the virtual reality intervention in this study outperformed conventional center-based activities in enhancing physical fitness and quality of life.

Section 3: The impact of virtual reality interactive game intervention on the quality of life of the elderly

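### No fall, fall-risk or adverse-event result is reported after baseline in either arm, so the Discussion's statement that the movements lowered the risk of falls during play has no data behind it

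*Combined protocol and SAP*

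**What the plan says.** Falls dominate the background (Chapter 1, Section 1; Chapter 2, Section 1). The stated objective and hypothesis (Chapter 1, Sections 2 and 3) are physical fitness and quality of life.

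Chapter 3, Section 5 places the fall risk assessment in the pre-test: "Both groups underwent pre-tests befor the intervention, which included a fall risk assessment, functional fitness assessment, and quality of life satisfaction survey". It describes no instrument for it. The follow-up visit is not itemised; the text says only that "post-tests were conducted to measure the effectiveness of the intervention". Chapter 3, Section 4 names what is measured repeatedly: "Functional physical fitness and quality of life assessments were conducted for both groups befor and after each session". Falls are not on that list.

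In the analysis plan (Chapter 3, Section 6) falls appear once, in a chi-squared check of baseline homogeneity that includes "experience of falling in the past year between the two groups".

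On safety during sessions, the Exercise Protocol provides blood pressure readings beforehand, supervision and a stopping rule: "In case of any discomfort during the activity, the training was immediately halted". It does not say that such events are recorded.

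In the results, the opening of Chapter 4 says of the VR arm that "five participants were absent for over one-third of the sessions (12 sessions) due to health issues or personal preferences". Chapter 5, Section 2 says that raising the arms and stretching in time with the body "effectively maintained body balance, reducing the risk of falls during" the game.

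**The concern.** The VR arm averaged 77.7 years. Its participants leaned forward, backward and sideways in a competitive game, in one stage from a slight squat. The hazard was foreseen: participants with weaker legs could hold a chair back. A reader would expect some count of falls, halted sessions or health-related withdrawals by arm, and there is none.

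The losses do not fill the gap. The five VR absences pool health with preference. The two control exclusions have no underlying reason given. The 14 exclusions among the 84 recruited mix personal reasons with illness and are not split by arm. A reader cannot tell whether any of these were harms.

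The report also encourages community centres to adopt such games, and its limitations section covers aircraft colours and connection delays but not harms. Next to a favourable phrase about falls, that silence may be read as evidence of safety.

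**Working it through.** **1. Where falls appear, stage by stage.**
- Pre-test: fall risk assessment and past-year fall history (Chapter 3, Section 5; Table 3).
- Sessions: a stopping rule and precautions, with no event recording described (Chapter 3, Section 4).
- Post-test: contents not itemised; only fitness and quality of life are named as repeated.
- Analysis plan: baseline homogeneity only (Chapter 3, Section 6).
- Results: Tables 4 to 7 contain BMI, fitness tests and quality-of-life domains only.

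**2. The one fall figure reported, reproduced from Table 3.**
- Test group: (6 + 1)/30 = 23.3%. This matches "Seven individuals (23.3%) reported experiencing falls in the past year", although the running text there labels the group as control.
- Control group: (5 + 3)/33 = 24.2%, as stated.
- Together: 15/63 = 23.8%. Fisher's exact p = 1.00.

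**3. The nearest proxy.** The row labels of Tables 5 and 6 are shifted against Table 4. The sixth row of Table 5 carries a physical quality-of-life label, but its pre-test values (8.5 ± 3.2 and 8.4 ± 3.6) are the up-and-go values of Table 4. The third to fifth rows likewise match the p-values that the text gives for the step test and the two reach tests. Realigned, the up-and-go went from 8.5 to 8.3 in the test group and from 8.4 to 8.2 in the control group. The ANCOVA gives F = 0.667, p = 0.418, partial eta squared 0.011. This does not support a lower fall risk.

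**4. What counting falls could show.** The documents give no on-study fall rate, so this is an illustration. Assumptions: constant hazard, and an annual faller proportion p between 23.8% (baseline, step 2) and 30% (Chapter 1, Section 1).
- 12-week risk = 1 − (1 − p)^(12/52): 6.1% to 7.9%.
- Expected fallers among 33 controls: 33 × 0.0608 = 2.0 to 33 × 0.0790 = 2.6.
- Power to detect a halving, 33 against 30, two-sided 5%, normal approximation: Φ[(Δ − 1.96·SE₀)/SE₁], with SE₀ pooled under no difference and SE₁ unpooled.
  - At 6.1% against 3.0%: (0.0304 − 1.96 × 0.0530)/0.0521 = −1.41, power 8%.
  - At 7.9% against 4.0%: (0.0395 − 1.96 × 0.0600)/0.0589 = −1.33, power 9%.
- For 80% power: about 738 per arm (at 6.1%) or 560 per arm (at 7.9%).
- If no VR participant had fallen, the one-sided 95% upper limit would be 1 − 0.05^(1/35) = 8.2% for the 35 enrolled, or 1 − 0.05^(1/30) = 9.5% for the 30 analysed.

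Even complete counts could therefore describe safety but not establish a reduction in falls.

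**The case against.** The strongest reply is that falls were never an outcome. The aims are fitness and quality of life, and the abstract and Chapter 6 claim nothing about falls. A 70-person, 12-week study could not have tested them. Precautions were in place: exclusion for mobility impairment, dizziness and unstable conditions, supervision, blood pressure checks and chair support. All of this stands, and it rules out criticising the study for lacking a fall endpoint. Precautions, however, are not event records, and they do not supply data for the Discussion sentence.

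Three stronger readings are tempting, and the documents do not support them.
- *The report claims the game reduces falls.* The sentence is limited to falls during play and is about the arm and body movements. The broader phrase in Chapter 2, Section 3 summarises cited literature.
- *Falls were never recorded.* The post-test is not itemised, and the figures and consent form are not in the text available. What can be said is that no such result is reported.
- *Several falls in the game went uncounted.* At the rates in the working, 70 × 0.0608 = 4.3 to 70 × 0.0790 = 5.5 participants would be expected to fall over 12 weeks, but at any hour and anywhere. Sessions fill 36 of 84 × 24 = 2,016 hours (1.8%). At a uniform hazard that is 35 × 0.0608 × 0.018 ≈ 0.04 to 35 × 0.0790 × 0.018 ≈ 0.05 in-session fallers in the VR arm. Exercise may raise that hazard, but the documents give no figure. Nor do they describe leaning in eight directions: that is where objects appear on the screen.

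**Conclusion.** The point holds as a matter of safety reporting and of one Discussion statement. After baseline, neither arm has a reported fall, fall-risk or adverse-event result. The phrase on fall risk during play therefore rests on no reported data, and the up-and-go result (p = 0.418) does not support it. The statement about reporting rests on the readable methods and Tables 2 to 7. The p-value rests on the label realignment, which the matching baseline values and the text support. The power of 8% to 9% rests on the assumed annual rates and constant hazard, and the normal approximation is rough at two to three expected events per arm. The fitness and quality-of-life results are not affected.

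**What to change.** **In the plan, and in any repeat or extension:**
- Ask the Table 3 fall question again at post-test in both arms, reworded to cover the time since the pre-test.
- At each session, in both arms, record falls (using the definition in Chapter 2, Section 1), sessions halted for discomfort, and absences for health reasons, kept separate from absences by preference.
- Report these as descriptive counts by arm for everyone who started, not only the 63 analysed, with no between-arm test.

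**For the completed cohort:**
- Report any existing session or absence records by arm, including the reasons for the five VR and two control losses.
- If there are none, delete the phrase on fall risk in Chapter 5, Section 2 and state in the limitations that falls and adverse events were not reported.

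**Cost:** one repeated question, and a few marks at a contact where blood pressure is already taken and attendance must already be known. The documents describe no attendance form, so the ease of adding marks is an assumption. People who stop attending would need to be contacted for the post-test question. The counts will be small and imprecise, and the favourable statement is lost unless records support it.

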feedback to complement each other. These games provide training for coordination, enhance reaction movements, and improve balance abilities, thereby increasing the willingness of the elderly to engage in physical activities. It has been found that these interventions are beneficial in preventing falls among community-dwelling elderly individuals. Constructing simple task-based games not only motivates the elderly but also enhances their enjoyment and morale, and even reduces anxiety (Lim et al., 2015; Chen et al., 2015; Llorens et al., 2016; Neri et al., 2017; Chen, Hu, Wang, & Lin, 2018; Huang et al., 2019; Hsu & Lin, 2020). However, current interactive games on the market are limited by space constraints, allowing only 1-2 individuals to engage simultaneously in the same space. Therefore, establishing an interactive game mode using virtual reality that enables multiple participants to engage in exercise together fosters interaction and communication among participants. Through cooperation, support, competition, and communication, this approach not only increases the frequency of interactions between the elderly and others but also enhances the willingness of the elderly to participate in exercise, effectively training balance abilities, and maintaining the overall satisfaction of their quality of life.

Section 2 Research Objectives

[figure not shown]
The purpose of this study is to validate the effectiveness of virtual reality interactive gaming exercises in improving the physical fitness of the elderly and enhancing their quality of life.

Section 3 Research Questions and Hypotheses Research Questions:

Does intervention with virtual reality interactive gaming exercises effectively improve physical fitness and quality of life among community-dwelling elderly individuals?

Hypotheses:

The use of virtual reality interactive gaming exercises contributes to improving physical fitness and quality of life among the elderly.

Section 4 Conceptual Architecture

Figure 1 Conceptual architecture diagram

Literature Review

Section 1: Falls and prevention among the elderly

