	protoct	posttast	difference	t value (p)	protost	nasttast	difference	t value (p)
	pretest	posttest	(Pre-test-P	或	pretest	posttest	(Pre-test-P	or
			ost-test)	S value (p)			ost-test)	S value (p)
	Mean ±	standard	deviation	-	Mean ±	standard	deviation	-
BMI	27.0 ± 3.5	26.9±3. 6	0.1±1.0	16.5 (0.741)	25.4 ± 3.8	25.3±3.7	0.1±0.4	75 (0.071)
30 seconds sit and stand	16.3±4.6	17.1±4. 4	-0.9±3.1	-56.5 (0.174)	17.7±5.2	18.5±4.9	-0.8±1.5	-83.5 (0.001)
The seat body bends forward (right)	96.0±20.7	121±25. 7	-26.6±31.2	-4.67(<0.001) §	92.5±25.4	98±20.2	-3.8±15.0	-1.47(0.151) §
The seat body bends forward (left)	2.9±10.1	7.3±9.6	-4.4±7.4	-140 (<0.001)	2.6±12.0	2.9±12.3	-0.3±2.8	0 (1.000)
Get up and walk Around at 2.4 meters	1.2±11.2	5.9±9.6	-4.9±8.1	-3.29 (0.003) §	1.4±13.4	2.9±13.2	-0.2±1.5	-0.79(0.433) §
Physiological quality of life	8.5±3.2	8.3±2.4	0.2±2.9	33 (0.507)	8.4±3.6	8.2±3.4	0.1±0.7	39 (0.384)
Psychological quality of life	10.8±1.4	11.1±1. 4	-0.1±0.4	-1.31 (0.202) §	11.4±1.5	11.3±1.4	0.0±0.1	1.00(0.325) §
Quality of social life	11.1±1.8	11.3±1. 7	-0.2±0.3	-18 (0.008)	11.7±1.8	11.7±1.9	-0.0±0.1	-0.5 (1.000)
Environment quality of life	11.2±1.9	11.3±1. 8	-0.1±0.4	-1.5 (0.500)	11.4±1.1	11.4±1.1	0.0±0.0	_*
The seat body bends forward (right)	10.6±2.2	10.6±2. 2	-0.0±0.1	-1.5 (0.500)	10.3±2.0	10.3±2.0	0.0±0.0	_*

§The Wilcoxon sign test is used, and the rest uses the dependent sample t test.

3. Comparison of Post-test between Experimental and Control Groups

Due to significant differences in demographic data and pre-test assessments between the experimental and control groups, particularly in the education level variable, and considering age as an important control variable, analysis of covariance (ANCOVA) was conducted to compare the post-test scores between the experimental and control groups. Age, education level, and pre-test scores were controlled for in the analysis. Intention-to-treat analysis was used.

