The results of ANCOVA analysis (Table 6) revealed that the post-test scores of the experimental group were significantly higher than those of the control group in five assessment outcomes, including the 2-minute step test (p < 0.001), right chair sit and reach (p = 0.010), left chair sit and reach (p = 0.002), psychological quality of life (p = 0.033), and environmental quality of life (p = 0.048). Additionally, the differences in fitness (except for the 30-second chair stand test) and quality of life had effect sizes (partial eta squared) ranging from 0.011 to 0.267, indicating moderate to substantial intervention effects. These results suggest that the intervention in this study was more effective in improving the aforementioned fitness and quality of life compared to regular community activities.

	StatisticsF /(p)	effect size (partial eta
		squared)
BMI	0.195 (0.661)	0.003
30 seconds sit and stand	0.015 (0.904)	0.000
The seat body bends forward (right)	21.154 (<0.001)	0.267
The seat body bends forward (left)	7.091 (0.010)	0.109
Get up and walk Around at 2.4 meters	10.294 (0.002)	0.151
Physiological quality of life	0.667 (0.418)	0.011
Psychological quality of life	0.956 (0.332)	0.016
Quality of social life	4.766 (0.033)	0.076
Environment quality of life	1.405 (0.241)	0.024
The seat body bends forward (right)	4.080 (0.048)	0.066

Table 6Post-test comparison between the experimental group and the

control group

Note: This analysis uses ANCOVA to control the pretest scores and other significant influencing factors

in the pretest. The control variables include: age, education level, and pretest scores of each variable.

Section 3: Analysis and Comparison of Quality of Life Questionnaire

Upon statistical analysis of pre-test and post-test scores (Table 7), it was found that in the experimental group, there was a difference of 0.4points in the physical domain (p = 0.202), no difference in the psychological domain (p = 0.008), a difference of 0.2 points in the social relationships domain (p = 0.500), and no difference in the environmental domain (p = 0.500). In contrast, in the control group, there was a difference of 0.4 points in the physical domain (p = 0.325), no difference in the psychological domain (p = 1.000), and no difference in the social relationships and environmental domains. The results indicate a significant change in the quality of life in the physical domain for the experimental group.

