Table 7 Analysis and comparison of pre- and post-test on the quality of life within the group after the experiment

		Test gro	up (N=30)			Control g	group (N=33)	
	pretest	posttest	score difference	t value (p)	pretest	posttest	score difference	t value (p)
		(Pre-tes	(Pre-test-	i value (p) prefess	pretest	lest positest	(Pre-test-	i value (p)
			Post-test)			Post-test)	_	
	Mean	\pm standard of	leviation	_	Mean	\pm standard	deviation	_
Physiological	10.0 + 1.4	11.1±1.4	0.1+0.4	-1.31	11 4 1 5	112114		1.00
quality of life	10.8±1.4 11	11.1±1.4	-0.1±0.4	(0.202)	11.4±1.3	11.3±1.4	0.0±0.0	(0.325)
Psychological	11 1 1 1 0	11.3±1.7	-0.2±0.3	-18	11 7 1 0	11.7±1.9	$0.0{\pm}0.0$	-0.5
quality of life	11.1±1.8	11.3±1.7	-0.2±0.3	(0.008)	11./±1.8	11./±1.9	0.0±0.0	(1.000)
Quality of	11.2+1.0	11 2 1 1 0	0.1 ± 0.4	-1.5	11 4 1 1 1	11 / 1 1 1		_*
social life	11.2±1.9	11.3±1.8	-0.1 ± 0.4	(0.500)	11.4±1.1	11.4±1.1	0.0 ± 0.0	_
Environment	10 (12 2	10 + 2 2	0.0 ± 0.1	-1.5	10.2 + 2.0	10.2 + 2.0		_*
quality of life	10.6±2.2	10.±2.2	0.0±0.1	(0.500)	10.3±2.0	10.3±2.0	0.0±0.0	_

*Since all subjects have the same score, the t test cannot be performed.

Chapter 5: Discussion

Section 1: Exploration of the Application of Virtual Reality Interactive Games in Community Care Centers

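### No primary outcome and no multiplicity control: the psychological and environmental quality-of-life claims (p = 0.033 and 0.048) fail Holm and Benjamini-Hochberg at 0.05, even within the four domains alone

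*Combined protocol and SAP*

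**What the plan says.** The hypothesis (Chapter 1, Section 3) is that the game "contributes to improving physical fitness and quality of life among the elderly". The two constructs are joined and neither is ranked above the other. Chapter 3, Section 5 lists four fitness tests and the four WHOQOL-BREF domains. BMI appears there as basic participant information, not as an outcome. The sample-size paragraph (Chapter 3, Section 2) uses a generic effect size of 0.5 that is tied to no outcome.

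Section 6 of Chapter 3 gives the only decision rule: "A significance level of p < .05 will be used to determine statistical significance". The text available for review contains no primary outcome, hierarchy or adjustment.

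In Chapter 4, Table 6 has ten ANCOVA rows, because sit-and-reach is split into right and left and BMI is added. The text reports that post-test scores in the experimental group were "significantly higher than those of the control group in five assessment outcomes". Two of the five are psychological (p = 0.033) and environmental (p = 0.048) quality of life. Both are carried into the abstract and Chapter 6 as significant improvements.

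**The concern.** With nine or ten tests each held to 0.05, some nominally significant results are expected by chance. The plan gives no way to tell which results were meant to carry the conclusion. Results just under 0.05 are the most exposed, and both quality-of-life findings are of that kind.

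Quality of life is one of the two constructs in the hypothesis, so half of the stated conclusion is at stake. The effects are also small, and for the environmental domain the mean change in Table 7 rounds to zero in both groups. The Table 7 footnote says of the control-group cells left blank for the social and environmental domains: "Since all subjects have the same score, the t test cannot be performed".

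**Working it through.** **1. Inputs and reproduction of Table 6.** The printed row labels do not match the text: 0.033 stands beside social quality of life, and 0.048 beside a second right sit-and-reach row. I assign values by row order as in Table 4, which agrees with the Chapter 4 text. The analysis used 30 + 33 = 63 participants. With an intercept, group, age, education as one term and pre-test score, the error df is 63 − 5 = 58. This df is inferred, but it reproduces the table. With p = P(F(1,58) > F) and partial eta squared = F/(F + 58):

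| Outcome | F | p (recomputed) | p (printed) | Partial eta squared |
|---|---|---|---|---|
| 2-minute step | 21.154 | 0.000023 | <0.001 | 21.154/79.154 = 0.267 |
| Left sit-and-reach | 10.294 | 0.0022 | 0.002 | 0.151 |
| Right sit-and-reach | 7.091 | 0.0100 | 0.010 | 0.109 |
| Psychological | 4.766 | 0.0331 | 0.033 | 0.076 |
| Environmental | 4.080 | 0.0480 | 0.048 | 0.066 |

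The other five printed p-values also reproduce within 0.001: social 0.241, physical 0.332, up-and-go 0.418, BMI 0.661, chair stand 0.904.

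**2. Chance of a false positive if no effect exists.**
- Either direction, independent tests: 1 − 0.95^9 = 0.370; 1 − 0.95^10 = 0.401. Four domains only: 1 − 0.95^4 = 0.185.
- False benefit only: 1 − 0.975^9 = 0.204; 1 − 0.975^10 = 0.224.
- The documents give no correlations between outcomes. Assuming a common correlation of 0.3 to 0.5 for nine tests (simulation, 500,000 draws), the figures fall to about 27–33% (either direction) and 14–17% (benefit).

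**3. Adjusted p-values.** Holm multiplies the k-th smallest of m p-values by m − k + 1. Benjamini-Hochberg (BH) multiplies it by m/k. Both then enforce monotonicity.

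| Family | Holm, psychological | Holm, environmental | BH, psychological | BH, environmental |
|---|---|---|---|---|
| Ten | 0.033×7 = 0.231 | 0.048×6 = 0.288 | 0.033×10/4 = 0.083 | 0.048×10/5 = 0.096 |
| Nine | 0.033×6 = 0.198 | 0.048×5 = 0.240 | 0.033×9/4 = 0.074 | 0.048×9/5 = 0.086 |
| Four domains | 0.033×4 = 0.132 | 0.048×3 = 0.144 | 0.096 | 0.048×4/2 = 0.096 |

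Hochberg and Hommel also fail in all three families (smallest value 0.099). The most lenient variant tried, adaptive two-stage BH, gives 0.0495/0.058 over nine tests but 0.058/0.067 over ten. If the printed Table 6 labels were right instead, the four domains would have p = 0.418, 0.332, 0.033 and 0.241. The 0.033 would still fail (0.033×4 = 0.132), and the environmental domain would not be significant even unadjusted.

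**4. Fitness results.**
- 2-minute step: Holm 0.0002 over nine or ten.
- Left sit-and-reach: Holm 0.002×8 = 0.016 (nine), ×9 = 0.018 (ten), ×4 = 0.008 (five fitness tests).
- Right sit-and-reach: BH 0.010×9/3 = 0.030 (nine) and 0.033 (ten); Holm 0.010×3 = 0.030 within fitness, but ×7 = 0.070 (nine) and ×8 = 0.080 (ten).

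**5. Size of the quality-of-life changes (Table 7).** The environmental change prints as 0.0 in both groups, so each is below 0.05 in absolute value and the groups' changes differ by less than 0.10. Against the smaller baseline SD of 2.0 that is under 0.05 SD. The psychological change in the experimental group is 0.2 points against an SD of 1.8, or 0.11 SD.

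**The case against.** The arithmetic is not in dispute. The strongest reply is that the hypothesis concerns quality of life as a whole, and two of four domains below 0.05 is itself unusual. Its probability is 1 − 0.95^4 − 4×0.05×0.95^3 = 0.014 if the domains are independent, and roughly 2–3.5% at correlations of 0.3 to 0.5. Fisher's combination of the four p-values gives 0.022 under independence and about 0.035–0.054 at those correlations. So a construct-level verdict depends on the method. This stands, but such a test is post hoc and borderline, and it supports neither named domain. The conclusions name the domains.

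Three further points have force:
- The 37–40% figure takes every effect as null. If two or three fitness effects are real, six or seven nulls remain, giving 26–30% under independence. Left and right sit-and-reach are also two halves of one listed test. The verdict rests on the adjusted p-values, which do not depend on this figure.
- The 0.048 may be unsound before any adjustment. With almost no one's environmental score changing, the ANCOVA assumptions are doubtful. That weakens the claim further.
- Table 6 shows all ten contrasts, nulls included, so outcomes were not hidden. The fault lies in the rule and the conclusions drawn from it.

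Both quality-of-life results would pass BH at a 10% false discovery rate, but the plan's only stated threshold is 0.05.

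**Conclusion.** The concern holds. Under the plan's single unadjusted threshold, two quality-of-life results are presented as established that fail Holm and BH at 0.05 whether the family is ten tests, nine, or the four domains. Holm values run from 0.132 to 0.288 and BH values from 0.074 to 0.096. The one exception is psychological quality of life under adaptive BH over nine tests (0.0495), which disappears when BMI is counted.

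This rests on the p-values as the Chapter 4 text assigns them, and on the printed statistics being correct. The false-positive rates rest on independence or on the assumed correlations.

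The fitness results are sturdier against multiplicity: 2-minute step and left sit-and-reach pass in every family above, right sit-and-reach only in some. They are still not confirmatory. The adjustment comes after the data. The planned model adjusted for pre-test score only, whereas in the analysis "Age, education level, and pre-test scores were controlled for in the analysis", a choice made after the baseline comparison. And "statistical analysis was conducted on data from 30 participants in the experimental group and 33 participants in the control group", that is 63 of 70, although Chapter 3, Section 2 did foresee excluding participants with missing tests or long inactivity. This is a matter for correction and does not call for repeating the trial.

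**What to change.** - Add a column of adjusted p-values (Holm, for example) beside the raw ones in Table 6. State in one sentence which family was used and that the adjustment was chosen after the data were seen.
- Remove the claim of significant improvement in psychological and environmental quality of life from the abstract and Chapter 6. Report those domains as exploratory, with raw and adjusted p-values.
- Describe the fitness results that pass as robust to adjustment, not as confirmed.
- Check the row labels of Tables 5 and 6 against the source output and correct them where they are shifted.
- Reconcile Table 5 before relying on the fitness results. By row order, control left sit-and-reach goes from 1.4 to 2.9 (difference −1.5) but −0.2 is printed. The 2-minute step goes from 96.0 to 121 (−25.0, printed −26.6) in the experimental group and from 92.5 to 98 (−5.5, printed −3.8) in controls.

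The cost is one column, one sentence, corrected tables and reworded conclusions. No new data are needed. The price is fewer claims.
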